The main purpose of this study is to characterize adolescents with chronic nausea through non-invasive gastric motor function and autonomic tests, and subsequently evaluate brain connectivity changes induced by auricular neurostimulation in functional gastrointestinal disorders (FGIDs). Functional nausea is a poorly understood condition that is difficult to manage due to lack of diagnostic testing and targeted therapies. Symptoms often overlap with those of gastric motor disorders such as delayed gastric emptying (gastroparesis) and poor gastric compliance. We have recently demonstrated safety and efficacy of auricular neurostimulation for the treatment of FGIDs. Functional magnetic resonance imaging (fMRI) is an established technique for studying brain networks and their connections. fMRI-BOLD (blood oxygen level dependent) signals detect changes in blood flow as a measure of brain activity. Resting state functional connectivity (rsFC) analysis is based on studying the functional organization of large-scale brain networks when a subject is not engaged in any mental task. Certain brain regions have greater coherence of neural activity as measured by the spontaneous fluctuations of the fMRI-BOLD signal. Studies of adult patients with a variety of chronic pain conditions show altered resting state brain network activity.¹⁻⁴ There is convincing data that baseline or rsFC between brain networks is dysregulated in patients with FGIDs.^{5,6} Our group has recently reported similar findings in children with irritable bowel syndrome.⁷ The amygdala is a limbic brain structure involved in emotions, fear, anxiety and processing of visceral sensations. The medial prefrontal cortex (mPFC) interacts with the amygdala to mediate the behavioral responses to various stimuli.⁸ We have recently demonstrated efficacy of non-invasive peripheral neurostimulation of the external ear in adolescents with FGIDs (IRB ID# 689519-17) (unpublished data). Preliminary animal studies from our group show significantly decreased neuronal signaling in the amygdala after auricular neurostimulation. The current proposal will phenotype patients with chronic nausea into various subgroups and then investigate intrinsic resting state brain connectivity in the functional nausea subgroup compared to irritable bowel syndrome and healthy controls before and after auricular neurostimulation therapy.

B. SPECIFIC AIMS / HYPOTHESIS

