Functional gastrointestinal disorders (FGIDs) affect a large percentage of children and negatively impact quality of life.⁹ The childhood prevalence is rising and based on a European study, the annual cost per patient is approximately \$2800.^{10,11} In adult patients with irritable bowel syndrome (IBS), the annual direct cost is estimated at \$1.35 billion.¹² Our recently published study showed that over 50% of children with FGIDs suffer from chronic nausea.¹³ Most of them have a diagnosis of IBS or functional abdominal pain. The nausea is seldom recognized or targeted therapeutically. Nausea in children cause disability and frequent school absences. In most cases, the nausea is deemed functional, without a known cause and without clear understanding of mechanisms. Pharmacotherapy is therefore empiric and the typical drugs used are centrally acting agents such as tricyclic antidepressants, suggesting the involvement of higher brain centers. In children, these drugs still have marginal efficacy compared to placebo^{14,15} and alternative strategies are generally as effective.¹⁶ A recent systematic review concluded there is no evidence to support pharmacologic therapy in pediatric FGIDs.¹⁷

No prospective studies exist that characterize functional nausea (FN) clinically or mechanistically. FGIDs are currently defined using symptom criteria (Rome criteria) rather than through a mechanistic understanding of their pathophysiology.¹⁸ Symptoms of FN often overlap with foregut motility disorders such as delayed stomach emptying (gastroparesis) and reduced stomach compliance (a 'stiff stomach') and are difficult to distinguish clinically. Current testing for gastric motor disorders is very limited in children, with lack of pediatric norms, using tests that expose children to radiation (nuclear gastric emptying scintigraphy). Non-invasive tests such as the ¹³C gastric emptying breath test (a non-radioactive isotope) has recently been studied in children and correlates well with scintigraphy.¹⁹ Similarly, the nutrient drink test (NDT) is an easy and non-invasive method that has been used in children to test sensitivity to gastric distention and impaired accommodation.^{20,21}

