One of the primary concerns in interpreting fMRI data obtained in children and in making comparisons across age groups involves the significant developmental changes in brain morphology that occur during childhood and adolescence. Although the majority of brain growth occurs prior to the age of 5 years, it has been estimated that approximately 5-8% of cerebral growth occurs between the age of 5 years and adolescence.⁴¹⁻⁴⁴ Furthermore, brain maturation proceeds at different rates in different regions of the brain. Concerns have been raised regarding the possible effects of these developmental changes on the process of spatial normalization, which involves transformation of images to a common stereotactic space based on an adult-derived template. The latter process is necessary in order to make direct voxel wise comparisons across subjects and subject groups. Recent studies do support the feasibility of making such comparisons within a common stereotactic space, suggesting that anatomical differences between the atlas transformed brain morphology of children (aged 7 to 8 years) and adults are minimal, relative to the level of resolution possible with current functional imaging and that would not result in spurious functional differences.^{45, 46} This study will include only adolescents who are at least 12 years of age, further minimizing any potential developmental effects.

Study Population

80-100 adolescents with chronic nausea and a subgroup of 15 patients with IBS as well as 15 healthy controls, between ages of 12-18 years, will be enrolled. All subjects will undergo gastric motor function and HRV testing at baseline followed by four weeks of auricular neurostimulation or sham therapy. By definition, all adolescents in this study will have no clear explanation for their symptoms after undergoing medical workup per standard of care.

Inclusion Criteria (Nausea and IBS Groups):

- Children aged 12 years to 18 years who provide written assent and whose parents provide written permission for participation

- English-speaking and able to verbalize their condition and concerns about nausea, pain and other symptoms
- Subjects will meet Rome IV criteria for functional nausea as determined by a pediatric gastroenterologist
- Subjects included in the IBS group will meet Rome IV criteria for Irritable Bowel Syndrome

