- Patients must have an intact external ear that is free of infection or severe dermatological conditions, have stable vital signs for their respective age, no history of seizures and no currently implanted electrical device
- Subjects included in the FN group include those who meet Rome IV criteria for functional nausea and have:
 - 1) autonomic imbalance with low vagal tone defined as baseline resting supine RMSSD value 2 or more standard deviations below the mean on HRV measurements, and
 - 2) normal gastric motor function (absence of gastroparesis or impaired accommodation). The gastric motor function and HRV tests will be compared to normative values obtained through a separate, ongoing, IRB-approved protocol (# 1030543-2)

Exclusion Criteria (Nausea and IBS Groups):

- Other pain-related diseases or somatization disorder
- Mental retardation or pervasive developmental disorder or epilepsy
- Psychosis
- Genetic or chromosomal disorders
- Pregnancy
- Subjects who admit to substance abuse during screening
- Patients with findings of peptic ulcer disease, H.pylori gastritis, celiac disease, inflammatory bowel disease, allergic disorders, or any chronic condition or medication that may cause nausea or pain
- Patients who are treated with opioids or who had any changes in their medical regimen in the past four weeks prior to study
- Patients with a history of allergy to adhesives
- Patients with a lactose intolerance

Study Design Overview

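### The IBS comparison group is not kept free of functional nausea, so the supporting FN-versus-IBS connectivity contrast is likely diluted and cannot be read as nausea-specific

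*Combined protocol and SAP*

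**What the plan says.** The opening statement of purpose sets out to study "resting state brain connectivity in the functional nausea subgroup compared to irritable bowel syndrome and healthy controls", before and after therapy. The scanning-protocol paragraph under Data Acquisition and Analysis (Section F) again names IBS patients, alongside healthy controls, as a comparison for the pre- and post-treatment scans. The Optional fMRI Sub-study plans 15 girls in the nausea group and 15 in the IBS group.

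Eligibility for both patient groups sits in one list in Section D, Inclusion Criteria (Nausea and IBS Groups). Three of its entries matter here:

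- With no group named: "Subjects will meet Rome IV criteria for functional nausea as determined by a pediatric gastroenterologist".
- For the IBS group: "Subjects included in the IBS group will meet Rome IV criteria for Irritable Bowel Syndrome".
- For the FN group: "Subjects included in the FN group include those who meet Rome IV criteria for functional nausea and have" two further features, namely resting supine RMSSD at least 2 SD below the mean and normal gastric motor function.

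The sub-study adds only that FN and IBS subjects satisfy the general criteria. The closest exclusion, also shared by both groups, is "Other pain-related diseases or somatization disorder". Section C gives the background figures: "over 50% of children with FGIDs suffer from chronic nausea", and "Most of them have a diagnosis of IBS or functional abdominal pain".

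**The concern.** A disease control helps only if it lacks the feature being studied. Here the IBS group may share functional nausea with the index group, either because the list requires it or because nothing prevents it. That pulls the expected FN-versus-IBS difference toward zero. A finding that FN resembles IBS could then reflect who was enrolled rather than how the two conditions behave. A difference that was found could not be credited to nausea either, because the groups are also selected differently on vagal tone, gastric motor function and IBS status. The post-treatment comparison with IBS patients has the same weakness.

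**Working it through.** **Step 1: which subjects does the nausea criterion cover?** The IBS and FN entries each name their group. The functional nausea entry names none and stands under a heading that covers both groups. The literal reading therefore applies it to IBS subjects. The Study Population paragraph, which speaks of adolescents with chronic nausea and a subgroup of 15 with IBS, does not settle whether the IBS patients come from the nausea cohort.

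**Step 2: does the lenient reading remove the overlap?** Suppose the entry was meant for the nausea group only. Neither the Section D inclusion and exclusion lists nor the sub-study criteria exclude functional nausea from the IBS group. IBS in the FN group is unclear, because the exclusion of other pain-related diseases may or may not reach it. A girl with IBS, functional nausea, low RMSSD and normal motor function meets both group definitions, and no rule says where she goes.

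**Step 3: how much overlap is plausible?** The plan gives no share for Rome IV functional nausea within IBS. Section C's figure, over 50%, is for chronic nausea across all functional gastrointestinal disorders. Used as a stand-in, 0.50 × 15 = 7.5 IBS subjects would be expected to have nausea. Under a binomial with p = 0.5, the chance of at least 5 of 15 is 0.94.

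**Step 4: is there a figure in the plan to reproduce?** No. The 15 per group comes with no effect size, SD or power. The power section refers Aim 2 to the fMRI analyses, which contain no power calculation.

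**Step 5: illustration of dilution.** The inputs are 15 v 15 (sub-study), 5% significance (Section O), and an assumed two-sided two-sample t-test. The detectable difference at 80% power by the normal approximation is √(2/15) × (1.960 + 0.842) = 1.02 SD. The t-based value is 1.06 SD, which is used below as the assumed true difference.

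Let q be the share of the IBS group that carries the full FN connectivity pattern. With a simple mixture and equal SDs, expected difference = (1 − q) × 1.06.

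| q | Expected difference (SD) | Power at 15 v 15 | n per group for 80% |
|---|---|---|---|
| 0 | 1.06 | 80% | 15 |
| 0.25 | 0.79 | 56% | 26 |
| 0.50 | 0.53 | 29% | 57 |

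Here q is not the share with nausea. If half the IBS group had nausea and half of those carried the pattern, q = 0.5 × 0.5 = 0.25.

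**The case against.** **No stated aim rests on this contrast.** Aim 2 compares FN with healthy controls. Aim 3 concerns active against sham, with change from baseline and resemblance to healthy controls. IBS appears as a comparator only in the purpose statement and the scanning-protocol paragraph. This stands, and it limits the point to a supporting comparison.

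**The groups are not interchangeable.** A reader might infer that the literal reading leaves no expected difference, or that any girl with both diagnoses could go into either group. The documents support neither. FN also requires low RMSSD and normal gastric motor function, and the hypothesised connectivity pattern is tied to low vagal tone. An IBS girl with nausea but without those features could not enter the FN group and need not carry the FN pattern.

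**The exclusion of other pain-related diseases could bar IBS from the FN group.** It could, if other means other than the group's own qualifying condition. The wording does not decide this, so a reader should not infer that the criterion cannot reach IBS. It does not address nausea in the IBS group under any reading.

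**Overlap can be measured.** The Rome IV questionnaire is completed at the Pre visit, nausea scales are repeated, and regressions of clinical scores on imaging measures are planned. This helps, and it makes the fix cheap. But collecting the data is not a rule for using it: nothing says how dual-diagnosis subjects enter the FN-versus-IBS contrast.

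**Barring IBS from the FN group may cost more than it gains.** Section C says most nauseated patients have IBS or functional abdominal pain, so strict exclusion could leave an unrepresentative FN group. This also stands, and it shapes the fix.

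**Conclusion.** The point holds for the supporting FN-versus-IBS comparison. Under the literal reading the IBS group must have functional nausea; under the lenient one it may, and Section C makes that likely. Either way the contrast is probably diluted and cannot be interpreted as specific to nausea. It is not necessarily zero, because the FN group is also selected on RMSSD and gastric motor function.

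The fall from 80% to 56% or 29% power is illustrative. It rests on an assumed true difference of 1.06 SD, an assumed t-test, and assumed shares of 25% and 50% carrying the full FN pattern. The documents supply none of these for this comparison.

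A reader might also infer that the trial's main conclusions are at risk. They are not: neither Aim 2 nor the active-versus-sham comparison on the Nausea Severity Scale depends on this contrast.

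**What to change.** - Limit the functional nausea entry in the Section D inclusion list to the nausea group.
- Define the IBS comparison group as meeting Rome IV IBS and not meeting Rome IV functional nausea, using the questionnaire already completed at the Pre visit.
- State whether the exclusion of other pain-related diseases is meant to cover IBS in the FN group.
- If subjects with both diagnoses are enrolled, flag them, leave them out of the FN-versus-IBS contrast, and report the overlap in both groups.
- Add a sensitivity analysis of FN subjects without IBS, rather than making IBS a mandatory exclusion from the FN group.

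This needs an amendment to the eligibility wording and a short analysis rule, with no new test. The cost is a smaller pool from which to fill the IBS group, or fewer than 15 per group in the contrast if dual-diagnosis subjects are enrolled and set aside.

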Specific aim #1: Define functional nausea (FN) as an entity subdivided by measures of arousal, anxiety and gastric motor function.

Hypothesis: Adolescents with chronic nausea form subgroups based on clinical, physiologic and psychological parameters: 1) FN: characterized by high anxiety and emotional arousal, autonomic imbalance/low vagal tone and absence of major foregut dysmotility, 2) gastroparesis, and 3) poor gastric compliance. We will separate FN from other groups by clinical questionnaires, autonomic tests (heart rate variability) and gastric motility tests (gastric emptying, accommodation tests).

Specific aim #2: Demonstrate that resting state functional brain connectivity is different in female adolescents with FN compared to gender and age-matched healthy controls.

Hypothesis: Adolescents with FN will have altered rsFC between brain regions associated with emotional arousal neurocircuits (amygdala) and the top-down regulation of these by the prefrontal cortex. There will be decreased resting state functional connectivity between the ventromedial prefrontal cortex (vmPFC) and amygdala in adolescents with FN compared to healthy controls.

Specific aim #3: Demonstrate that four weeks of auricular neurostimulation improves nausea while strengthening the vagal tone and the abnormal resting state brain connectivity in female adolescents with FN compared to baseline and to more resemble that of healthy controls.

Hypothesis: 3a) Compared to baseline (pre-stimulation), there will be reduction in nausea and concurrent symptoms in the active compared to sham neurostimulation group after 4 weeks of therapy. 3b) Active neurostimulation therapy will increase vagal tone compared to baseline and also increase the rsFC between the vmPFC and amygdala in female adolescents with FN.

C. BACKGROUND, SIGNIFICANCE, AND RATIONALE

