The SDT is a simple and non-invasive measure of sensation to gastric distention. It has good reproducibility and correlates fairly well with barostat studies of gastric accommodation.^{81,82 20} The maximum tolerated gastric volume and satiety is recorded after subjects ingest a nutrient formula at a predetermined rate until reaching maximal satiety (see protocol below). The volume ingested when reaching a satiety score of 5 corresponds to the maximal ingested volume (i.e. drinking capacity). The SDT measurements will be compared to normative data from a separate study. A drinking capacity (kcal) of <5th percentile for age and gender will classify a patient as impaired gastric accommodation.

Studies will be carried out on a separated day from the above GEBT, also in the morning after an overnight fast. Height and weight of subjects will be recorded prior to testing. Subjects will ingest a room temperature liquid nutrient drink (Ensure Original Vanilla; Abbott Laboratories, IL, U.S.) containing 220kcal per 237ml, 18% protein, 11% carbohydrates and 9% lipids. One of two beakers will be filled with the drink by a research coordinator or nurse at a rate of 30 ml/min. The subject will be instructed to ingest the drink at the filling rate by alternating the beakers. Every 5 min, they will be asked to score their satiety and symptoms of nausea, bloating, pain, burning sensation and vomiting on a scale 1-5: 1= no sensation; 2=first sensation; 3=mild sensation; 4=moderate sensation and 5= maximum sensation. The maximum tolerated gastric volume (kcal), i.e. drinking capacity, is recorded after subjects reach maximal satiety with a score of 5 at which point they will cease drinking. At the same 5 min intervals, subjects will also be asked to circle their nausea on a validated pictorial nausea severity scale (BARF scale) 0-10.⁸³ Twenty minutes after completing the test, the subjects will again score the above symptoms on scale 1-5. A research coordinator or nurse will assist the children with completing the scores and carefully explain symptoms such as satiety as their fullness and opposite of desire to eat.

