Prior to any study procedures, subjects will be carefully screened for any allergies to Spirulina, egg, milk, or wheat allergens, lactose intolerance as well as use of medications. Subjects will be instructed that some discomfort may be expected during the nutrient drink test. They will also be notified that they may experience symptoms of nausea, fullness, bloating or pain. However, since the test is designed to cease when maximum satiety is reached, we do not expect significant symptoms to occur.

Heart Rate Variability

HRV reflects the variability of the R-R interval in the electrocardiogram and its frequency domains.⁸⁴ HRV is an indirect measure of central autonomic control and an indicator of overall psychological well-being.⁸⁵ Reductions in resting HRV reflect decreases in vagal output. The high frequency range of HRV is considered representative of vagal (parasympathetic) activity and studies show altered vagal tone as measured by HRV in subjects experiencing nausea.⁸⁶ All subjects will undergo a 9 minute baseline HRV measurement (3 minutes sitting, 3 minutes standing and 3 minutes sitting) after 10 minutes of rest. This will be repeated 20 minutes into neurostimulation and following the end of therapy. Data will be compared to the healthy controls from IRB protocol (#1030543-5). Recordings will be performed supine, sitting and standing to assess baroreflex response. HRV indices such as Respiratory Sinus Arrhythmia (RSA), low frequency domains, low/high frequency ratio and the time domain RMSSD as a surrogate of vagal tone⁸⁴ will be analyzed using CardioEdit/Batch software. The RSA values will be the primary HRV outcome and compared to baseline pre-neurostimulation and previously collected normative data from age-matched, healthy controls.

Questionnaires:

All patients will complete the questionnaires listed below. Patients are allowed to skip any questions that they do not feel comfortable answering. A member of the research team will introduce each questionnaire and explain the instructions to each of them.

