The fMRI scans will be carried out using GE 3T short bore scanner. This scanner is located at the Froedtert Hospital. For each participant we will perform one baseline whole brain anatomical scan and one resting state fMRI scan before and after therapy. Healthy controls will have only one baseline fMRI scan. The healthy controls will also undergo a visual task where they are simply shown images while in the fMRI scanner. These images will be related to toilet training and this data will be used for healthy comparison data from separate study by our group (IRB #774802-6). We anticipate the whole session to last about 40 minutes. Echo planner images resolved to 64x64 pixels/slice at TR of 2s and echo time of 25 ms will be obtained.

Resting State Functional Connectivity MRI

Resting state functional connectivity (rsFC) analysis measures the temporal correlation between a predetermined seed region of interest and functionally related brain regions. After subgrouping and additional consenting, 15 post-pubertal female subjects classified as FN will undergo a 10 minute anatomical scan followed by a 6 min rsFC MRI scan at baseline prior to first EAD placement which is repeated after 4 weeks of therapy (after stimulator removed) (Table 1; post-neurostimulation #1). 15 female subjects classified as irritable bowel syndrome (IBS group) will undergo the same protocol. Resting state MRI scans will be performed per protocol below. The amygdala will be used as a seed region and the functional connectivity between the amygdala and PFC regions will be examined during rest at baseline. Data will be compared in treatment

responders (if possible) and non-responders in order to evaluate connectivity differences before and after therapy in these two groups.

Multimodal Imaging protocols

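### The functional-nausea cut-off of 2 SD below mean RMSSD names no scale; on raw values it under-selects if the norms are right-skewed, and nobody can meet it if the normative SD is at least half the mean

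*Combined protocol and SAP*

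**What the plan says.** Section D, Inclusion Criteria (Nausea and IBS Groups), requires two things of the FN group beyond Rome IV criteria: normal gastric motor function, and low vagal tone, defined as "baseline resting supine RMSSD value 2 or more standard deviations below the mean on HRV measurements". The reference is external: "The gastric motor function and HRV tests will be compared to normative values obtained through a separate, ongoing, IRB-approved protocol (# 1030543-2". The Heart Rate Variability text in Section F cites the same protocol number with a different suffix: "Data will be compared to the healthy controls from IRB protocol (#1030543-5". Neither place gives a normative mean, SD, sample size or distribution, and the criterion names no transformation, percentile or age and sex stratum.

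The two gastric rules in Section F are set as percentiles. Delayed emptying is a half-time above the 90th percentile of controls. For the drink test, "A drinking capacity (kcal) of <5th percentile for age and gender will classify a patient as impaired gastric accommodation".

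The Heart Rate Variability text lists "3 minutes sitting, 3 minutes standing and 3 minutes sitting" as the baseline recording. Later in the same paragraph it says that recordings are made supine, sitting and standing.

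Two parts of the plan depend on the classification. Section B, Aim 1, states that "Adolescents with chronic nausea form subgroups based on clinical, physiologic and psychological parameters" and names three: FN, gastroparesis and poor gastric compliance. Section F, Resting State Functional Connectivity MRI, plans to scan "15 post-pubertal female subjects classified as FN". Section E puts the pool to be phenotyped at 80-100 adolescents with chronic nausea.

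**The concern.** Two SD below the mean marks a fixed tail, 2.28%, only if the measure is normally distributed on the scale used. RMSSD is a root mean square, so it is bounded below by zero. The plan uses it as "low/high frequency ratio and the time domain RMSSD as a surrogate of vagal tone" but does not say how it is distributed. On a non-negative measure with a wide spread, mean minus 2 SD moves towards zero and then past it, and the rule selects fewer and fewer people.

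The FN label decides who enters the Aim 1 FN subgroup and who can be scanned as FN for Aim 2 and the imaging part of Aim 3. Too strict a cut leaves those parts short of patients for a reason of scale rather than biology. The plan projects no FN count that would show whether this happens.

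There is also a gap in the classification. A patient who meets Rome IV criteria, has normal gastric function and has RMSSD above the cut belongs to none of the three Aim 1 subgroups. The stricter the cut, the larger this group becomes.

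**Working it through.** The plan states no percentile, normative figure or expected FN count for this rule, so there is no figure of its own to reproduce. Everything below that uses a CV, a distribution or a patient reduction is an assumption, shown as a range.

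**Step 1: shape-free result.** Cut = mean − 2 SD = mean × (1 − 2 × CV). At CV 0.5 this is 0; above 0.5 it is negative. No positive RMSSD can then meet it, whatever the distribution.

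**Step 2: healthy subjects below the raw cut.** Set the normative mean to 1. For lognormal norms σ² = ln(1 + CV²) and μ = −σ²/2, and the share below the cut is Φ((ln(1 − 2CV) − μ)/σ). At CV 0.2, σ = 0.198 and μ = −0.0196, so z = (−0.511 + 0.0196)/0.198 = −2.48, a share of 0.66%. Normality would give Φ(−2) = 2.28%. Gamma norms serve as a second right-skewed shape.

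**Step 3: patients below the cut.** Let the patients' geometric mean be r times the norm, with the same log SD. On the raw cut the share is Φ((ln(1 − 2CV) − μ − ln r)/σ). With the 2 SD rule on ln RMSSD it is Φ(−2 − ln r/σ). At CV 0.2 and r = 0.7 the raw value is z = (−0.511 + 0.0196 + 0.357)/0.198 = −0.68, or 24.8%.

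| Normative CV | Raw cut ÷ mean | Healthy below raw cut, lognormal / gamma | Patients below raw cut, r = 0.7 / 0.5 | Patients below ln cut, r = 0.7 / 0.5 |
|---|---|---|---|---|
| 0.2 | 0.6 | 0.66% / 1.12% | 24.8% / 84.6% | 42.1% / 93.3% |
| 0.3 | 0.4 | 0.15% / 0.55% | 3.9% / 27.0% | 21.6% / 64.1% |
| 0.4 | 0.2 | 0.003% / 0.12% | 0.11% / 1.4% | 14.1% / 42.0% |
| 0.5 | 0 | 0 / 0 | 0 / 0 | 10.7% / 29.7% |

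On the ln scale the cut stays positive (0.66, 0.53, 0.43 and 0.35 times the mean at these CVs), and for lognormal norms it sits at the 2.28th percentile at every CV.

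**Step 4: set against the need.** Fifteen scans from a pool of 80-100 require 15/100 = 15% to 15/80 = 18.75% of the pool to be scannable FN females. The shares in the table come before the normal-motility requirement. As an illustration, suppose patients lie 1 log-SD below the norms and fail the gastric tests only as often as the controls would, independently, so that 0.90 × 0.95 = 85.5% have normal motility. The raw rule then yields 5-6 FN patients at CV 0.2, about 2 at CV 0.3, about 0.1 at CV 0.4 and none at CV 0.5. The ln rule yields 0.855 × Φ(−1) = 0.855 × 15.9% = 13.6% of the pool, or 11-14 patients. Both are counted before the sex, puberty and MRI filters.

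**The case against.** The strongest reply is that the serious part depends on numbers nobody outside the trial can see. The criterion does not say raw, and the separate normative protocol may already define RMSSD on a log scale or by stratum. The documents do not call RMSSD skewed. With tight norms (CV 0.1 to 0.2) the raw cut leaves 0.7-1.7% of healthy subjects below it, which is usable. If patients' vagal tone is as low as the hypothesis supposes, many could qualify: 24.8% at CV 0.2 with a 30% reduction, and 27.0% at CV 0.3 with a 50% reduction. A strict cut may also be deliberate for a low-vagal-tone phenotype. All of this stands, and it limits the claim to a range. It does not supply the missing scale. The Statistical Analysis section does allow transformations, but only to meet the assumptions of tests and models, and does not tie them to this criterion.

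A reader might infer that the 2.3rd percentile was the intended target; the text names none. A reader might infer that no supine recording is planned; the Heart Rate Variability text mentions one, so the posture statements conflict but the measurement is not shown to be absent. Nor can it be said that age was ignored, since that section calls the controls age-matched when it describes the RSA comparison.

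**Conclusion.** The rule as written is under-specified. Read literally, it is a poor choice of scale for a non-negative measure. One result needs no distributional assumption: on the raw scale nobody can qualify if the normative SD is at least half the mean. The rest is conditional on right-skewed norms, where the rule takes less than the nominal 2.28%. Depending on the assumed CV and patient reduction, the effect runs from modest to an empty FN group.

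A reader might go further and conclude that the trial cannot answer its treatment question. The documents do not support that. Section E randomizes the chronic nausea patients without restricting to FN, and the Statistical Analysis section sizes hypothesis 3a on about 40 per group and analyses vagal tone change in nausea subjects. Aim 1 is descriptive, and its two gastric subgroups have their own rules. The exposed parts are the FN subgroup of Aim 1, the 15 FN scans of an optional sub-study and the FN-specific claims.

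The posture conflict and the unclassified group stand without any assumed figure.

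**What to change.** - Restate the criterion as ln RMSSD at least 2 SD below the normative mean of ln RMSSD, or as the equivalent normative percentile (2.28th), from the same normative data, with age and sex strata where those data allow. Give the normative mean, SD and sample size, and say which data set they come from, since the protocol suffix differs between sections. The 2 SD stringency is kept. Moving to the 5th percentile used for the drink test would loosen the phenotype; that is a separate choice, not a correction of scale.
- Before scanning starts, project the number of eligible FN females against 15, using the actual norms and the baseline RMSSD values already collected. The log scale alone may not reach 15, as Step 4 shows.
- Reconcile the two posture statements in the Heart Rate Variability text with the supine value that the inclusion criterion requires, and confirm that patients and norms are recorded in the same posture.
- Report patients with normal gastric function and RMSSD above the cut as a separate, named group in Aim 1.

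The cost is one rewritten eligibility sentence, one short table of norms and one added row in the Aim 1 summary. No new measurements follow from the change of scale. The downside is that FN becomes a slightly less extreme group.
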